# Data Analysis and Monitoring

The primary endpoints, a VAS assessment of snoring and the Snoring Severity Scale will be analyzed using a two-sample *t*-test comparing the pre-study and post-study questionnaire results. The ANCOVA method may also be used to evaluate the impact of different variables, like age, weight, gender, or others, on the study results. There are no potential serious risks to patients, and no stopping criteria that need to be analyzed during the study.

In determining sample size, it was estimated that the device would produce a 15% improvement in snoring, as measured on the VAS. With a level of significance of p < 0.05 and a power of 80%, approximately 350 subjects will need to complete the study to generate statistically significant data. Assuming a 30% dropout rate for non-compliance with the study or the discovery of moderate to severe sleep apnea, 500 subjects will be enrolled in the study to ensure the study is adequately powered.

## Data Storage and Confidentiality

Data will be collected via a password-protected website and confidential email forms. The results will be securely stored in password-protected cloud storage and then downloaded onto a personal computer to be compiled in Excel. Once transferred to Excel, the data will also be placed into a password-protected file. This data will be available to the study coordinator alone, as the principal investigator is blinded (a precaution since he has a financial interest in the device). Subject identifiers will be necessary, but only the study coordinator will have access to the data with subject identifiers. These identifiers will be removed before any data or statistical analysis is conducted. The principal investigator will be provided the subject identifier and data for any patient that has an unexpected serious reaction to use of the device for analysis and response as well as notification of regulatory bodies and the investigational review board.

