## Potential Risks

One potential risk is overheating the moldable material when fitting. The device is placed in boiling water to make it pliable and then molded to the individual user. These 'boil and bite' mouthguards have been on the market for more than 40 years, and this device has no higher risk than these OTC products currently on the market. The product instructions are clear about instructing patients to ensure that the mouthpiece is at a suitable temperature prior to application.

A silicon strap on the device keeps the tongue from falling back, preserving the airway. It might be possible for this strap to break free and be swallowed. This is an unlikely risk, as it is held in place by two different attachment points, so even if one side of the strap were to break free, there would no longer be any stress on the other side of the strap, which makes it highly unlikely that both sides of the strap would break at the same time. During the 510k approval process for the Zyppah Boil and Bite, the FDA was presented with data showing the forces necessary to break the silicon strap. With more than 100,000 users of the product per year, there has not been a single reported or known incident where both sides of the strap have come off. However, even if the silicon strap were to break free, the silicon is inert and should not cause any health concerns if swallowed.

The device does not advance or adjust the position of the jaw, so there is no risk of TMJ issues or bite changes. The top and bottom halves of the device are locked together, preventing any jaw advancement.

One potential concern is the ability of the mouthpiece to pull out fillings or crowns. However, the device is made of a soft material with limited retentive abilities. With more than 100,000 users of the product, no known incidence of a filling, crown, or tooth being pulled out by the device has been reported. In addition, the device is made of the same material used safely for more than 40 years with mouthguards and other intraoral devices.

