Mouth or tooth soreness can also result from the use of any intraoral device. If a patient experiences any significant soreness, it is likely the result of an improper molding of the device to the teeth. The device can be re-molded up to three times to make sure a correct fit is generated. If the patient is unable to generate a correct fit and the tooth soreness persists, they are instructed to contact customer service and discontinue use. This risk is identical to that of other OTC mouthguards.

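### The only escalation rule turns on an undefined reaction that is both unexpected and serious, notification is described only through the financially interested principal investigator, and no listed form collects adverse events

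*Combined protocol and SAP*

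**What the plan says.** All references are to the combined protocol and SAP.

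**Who holds the data.** Data Storage and Confidentiality states: "This data will be available to the study coordinator alone". The reason given is that "the principal investigator is blinded (a precaution since he has a financial interest in the device".

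**When a case is escalated.** The same section makes one exception. The principal investigator is sent the participant's identity together with "data for any patient that has an unexpected serious reaction to use of the device for analysis and response". The investigator is also to use this material to inform regulators and the review board. The section defines neither of the two conditions. It gives no time limit, no independent assessor, and no direct route from the coordinator to the board.

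**Which harms are foreseen.** Potential Risks says: "One potential risk is overheating the moldable material when fitting". On the strap it says: "It might be possible for this strap to break free and be swallowed". It also discusses dislodged fillings or crowns, and soreness of the mouth or teeth. For users whose soreness persists and who cannot obtain a fit, the protocol says "they are instructed to contact customer service and discontinue use".

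**What is said about seriousness.** Data Analysis and Monitoring holds that patients face no potential serious risks and that no stopping criteria are needed.

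**What is collected.** Data Collection lists the post-study questionnaire as Attachments B, C and D: the VAS, the Snoring Severity Scale and STOP-BANG. Purpose and Background names safety, with efficacy, as what the study is to evaluate.

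**The concern.** Three weaknesses combine.

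- **The trigger is ambiguous.** A reaction must be both unexpected and serious. The harms the protocol discusses in advance are the ones a reader could most easily call expected, so the rule is least certain for the harms considered plausible.
- **The route sits awkwardly with the plan's own safeguard.** The investigator is kept from the data because of a financial interest, yet is the only described link to regulators and the review board.
- **Little brings an event to the coordinator.** No listed form asks about harm, and the one complaint contact described for a device problem has no stated link to the study data.

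At stake is the safety conclusion. The device is meant for sale without professional supervision, and participants fit it at home after softening it in boiling water. A low count of events would be hard to interpret if the plan does not secure that events are asked about, recorded and passed on.

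**Working it through.** No stated figure can be reproduced for this point. The check sets the sections side by side.

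**Step 1: the trigger.** Escalation requires *serious* AND *unexpected*. If either condition fails, the rule as written requires nothing. Neither condition is tied to a list or definition.

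**Step 2: apply it to a serious case of each named type.**

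| Named event | How the protocol describes it | If expectedness follows Data Analysis and Monitoring (no serious risk foreseen) | If expectedness follows Potential Risks (event named in advance) |
|---|---|---|---|
| Burn from hot material | No riskier than marketed OTC products | Unexpected: escalate | Expected: need not escalate |
| Strap detached and swallowed | Unlikely; inert material | Unexpected: escalate | Expected: need not escalate |
| Filling or crown pulled out | None known among more than 100,000 users | Unexpected: escalate | Expected: need not escalate |
| Soreness | Attributed to poor moulding; temporary | Unexpected: escalate | Expected: need not escalate |

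The same event gives opposite answers in all four rows. The text does not settle which column applies.

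**Step 3: who chooses.** The coordinator alone sees the data, so the coordinator decides, without a definition, whether a case reaches the investigator.

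**Step 4: what happens next.** Once passed on, the case goes to the investigator for analysis, response and notification. No parallel notice to the board is described.

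**Step 5: how an event reaches the coordinator.** Attachments B, C and D measure snoring bother, snoring severity and apnea risk. Data Collection mentions no adverse-event item. Customer-service contacts have no stated onward path. Costs to the Subject says the sponsor will pay uninsured costs of device complications, but not that those complications are recorded.

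**Step 6: how far a survey item alone would reach.** Data Analysis and Monitoring plans to enrol 500 with 30% dropout. 500 × 0.30 = 150 non-completers, and 500 − 150 = 350, which matches the stated number of completers. A question in the follow-up survey would therefore miss up to about 150 participants if none of them returns it. Forwarding of customer-service contacts is needed as well.

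**The case against.** The strongest reply is that being named as a potential risk is not the same as being expected in serious form. Data Analysis and Monitoring sees no serious risk, and Potential Risks and Protection against Risks present the named harms as minor, temporary or improbable. On that account a serious burn or a harmful swallowed strap would be unexpected, and the rule would fire. This reading is as tenable as the opposite one. A reader might infer that no serious event of a named type would be escalated, and might attach a number of missed cases. The documents support neither: the wording leaves the matter open, and no serious-event rate is given from which to count.

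A second reply concerns the conflict of interest. The first screen is the coordinator, for whom no financial interest is stated. Receiving one participant's data for a safety response does not open the pooled efficacy data, and the text does not say that notification must wait for the investigator's assessment. This stands in part: the precaution has a limited, disclosed exception and is not abandoned. It remains true that no other notification route is described.

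Third, a reader might infer that complaints to customer service never enter the trial's counts. The protocol is only silent on forwarding. Consent and contact pages were removed, and the device instructions are not in the text reviewed; any of these may give another reporting contact. The statements about routes therefore apply only to the text available.

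**Conclusion.** The point holds as a gap in definition, routing and capture. Under the present wording, a serious case of any of the four named types can be escalated or not according to which section the coordinator follows. The only described notification path runs through the person whom the plan shields from the data because of a financial interest. With no adverse-event item among the listed post-study forms and no stated link from customer service, the trial can under-count events.

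The size cannot be given as a number of events. Up to 500 participants are exposed to the gap, and the documents offer no rate to apply to them. The conclusion assumes that the pages and attachments not available contain no fuller reporting procedure; if they do, the protocol should refer to it. The change is worth making because it is cheap and bears on a stated purpose of the study, but it does not show that events would in fact be suppressed.

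**What to change.** 1. In Data Storage and Confidentiality, change the trigger to any serious event, whether or not expected, plus any mouth burn, strap detachment, or loss of a filling, crown or tooth. State what counts as serious. Reconcile the result with Data Analysis and Monitoring and with Potential Risks.
2. Have the coordinator send each such report to the review board at the same time as to the principal investigator.
3. Have customer service forward every contact from a study participant to the coordinator for entry in the study data.
4. Add a short adverse-event question to the post-study survey, and list it in Data Collection.

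Item 4 is needed because a wider trigger cannot act on events the coordinator never hears of. Item 3 is needed because non-completers will not answer the survey.

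The cost is a few sentences of protocol text, one instruction to customer service, one more survey item and a few more reports to the review board. The changes concern reporting and recording only; design and sample size are unaffected.

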## Transition from Research Participation

As this research study only asks patients to use the product as they would normally, subjects will continue with their use according to the device instructions, and are free to stop use at any time following the post-study survey after 10 days of application.

## Statistical Analysis

A two-sample *t*-test will be used to compare the results from the pre-trial and post-trial questionnaires. Statistical significant will be set at a 95% confidence level (p < 0.05).

## Risk/Benefit Assessment

# Definition of Significant Risk (SR)/Non-significant Risk (NSR) Study

Under 21 CFR 812.3(m), an SR device means an investigational device that: i) Is intended as an implant and presents a potential for serious risk to the health, safety, or welfare of a subject; ii) Is purported or represented to be for use supporting or sustaining human life and presents a potential for serious risk to the health, safety, or welfare of a subject; iii) Is for a use of substantial importance in diagnosing, curing, mitigating, or treating disease, or otherwise preventing impairment of human health and presents a potential for serious risk to the health, safety, or welfare of a subject; or iv) Otherwise presents a potential for serious risk to the health, safety, or welfare of a subject. An NSR device study is one that does not meet the definition for an SR device study

## Risk Category

The risk the research presents is minimal. The chance of harm or discomfort is not higher than subjects may experience in daily life. There are many over-the-counter mouthguards and intraoral devices on the market, with a safety profile that has been established for nearly 40 years. The probability and magnitude of potential harm is well within the routine dental examination of healthy persons.

In addition, this device has been used on the market (for a different application) for several years, and more than 100,000 users have demonstrated the low risk of this device. Should any complications occur, use of the device can immediately be discontinued.

There is a risk that the patient has undiagnosed OSA, but this risk is lowered by participating in the study and taking a survey to indicate the level of the risk. No additional risk is incurred by a patient with OSA.

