#### Study Design

Patients will enroll in the study online. The on-line experience has been carefully designed to mimic the experience of buying the device in a retail store or on a website without consulting a sleep professional or dentist. After filling out a short online questionnaire to determine their initial symptoms and signing the informed consent, the product and instructions will be shipped to them. The device is used for a period of 10 days in the clinical trial. An email prompting them to complete a follow-up questionnaire will be sent ten days after the device has been received. Upon completion of the follow-up survey, the cost of the device will be refunded to the patient, incentivizing completion of the study.

The surveys will ask the patients to qualitatively and quantitatively compare their snoring before use of the device and after 10 days of using the device.

As part of the follow-up survey, users will be asked if they self-identified (on the basis of the product instructions) as being at risk for OSA. If they answer positively, they will be asked about their response, including whether they sought medical care, enrolled in a sleep study, or discontinued use of the device.

A two-sample t-test will be used to analyze the change from the initial survey to the follow-up survey, with patients serving as their own controls.

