## Methods and Procedures

## Methods and Procedures

Subjects who are interested in reducing their snoring will be recruited online. In order to participate in the trial, they will complete a pre-trial questionnaire, as well as review and sign the Informed Consent.

Assuming they satisfy the Inclusion and Exclusion criteria and sign the Informed Consent (includes the inclusion/exclusion criteria), they will purchase the device for \$90. The intraoral device and patient instructions will be mailed to them (Attachment E).

Once the subject is able to participate in the study, the device is placed in boiling water to soften it. While still warm, the device is placed in the mouth and molded to the individual patient. This is the same procedure used with many intraoral mouthpieces and devices including the Zyppah Boil and Bite.

The subject will be asked to use the intraoral device each night for ten consecutive nights. After they have used the device for ten days, a follow-up survey will be emailed to the subject. The patient will respond to the questions in the survey. After they have completed the follow-up survey and returned it, the subject will receive a full refund for the cost of the device (\$90). This is intended to increase compliance with the protocol.

This study will also evaluate the response of subjects who are at high risk of obstructive sleep apnea. The product instructions will contain a brief questionnaire (Attachment D, STOP-BANG Survey) assessing the subject's risk for OSA. If they are determined to be high-risk by the self-administered questionnaire, they will be given the following options: 1) complete a full, overnight in-office sleep study, 2) complete a discounted in-home sleep study, or 3) discontinue use of the device and return it for a full refund. The response of these subjects will be monitored to see how they respond and whether they continue to use the device or seek medical attention to evaluate their risk of sleep apnea.

This is a non-significant risk study, and the only 'extra' requirements for this study are the completion of the pre-study and post-study questionnaires by the patient.

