# Data Collection

- Attachment A is the list of questions to gather personal information about the subject, including age, gender, weight, height and contact information. This will allow for the calculation of Body Mass Index (BMI), a well-known risk factor in both snoring and obstructive sleep apnea. This attachment also contains the Inclusion/Exclusion criteria, where potential subjects will be asked to review and certify that they meet the requirements of the trial (they will also see this information later in the process at the Informed Consent).
- Attachment B is the Visual-Analog Scale (VAS) asking potential subjects how much their snoring is bothering them and their partner (if applicable). The VAS method is commonly used and has been validated for patient satisfaction (Brokelman et al, 2012).
- Attachment C is the Snoring Severity Scale (SSS). This validated, three-question survey has been shown to accurately assess the severity of snoring and the risk for obstructive sleep apnea (Morris L et al, 2008)
- Attachment D is the Stop-Bang Assessment, which is the most frequent assessment used to determine the risk of sleep apnea. This 8-question survey has been validated as a risk assessment for moderate to severe sleep apnea (Nagappa et al, 2015).

The pre-questionnaire will consist of Attachments A, B, and C to establish a baseline. The postquestionnaire will consist of Attachments B, C, and D, also allowing the study to evaluate the response of subjects at high risk of OSA.

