# Alternatives to Participation

Participants have many other options to choose in trying to reduce or eliminate snoring. Nose strips, which attempt to increase the amount of air that can pass through the nasal passage, are available over-the-counter. Other intraoral devices designed to combat snoring are available as either over-the-counter or prescription devices. Simple lifestyle changes, including losing weight, avoiding alcohol

consumption prior to sleeping, and sleep position can also be effective for some patients with habitual snoring.

If the more serious condition of severe obstructive sleep apnea is suspected, patients are encouraged to go through a sleep study to conclusively diagnose sleep apnea. Sleep apnea can be treated with a CPAP machine, or with various other intraoral devices under the care of a sleep specialist or dentist.

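### The Risk Category statement on undiagnosed OSA holds for subjects who complete the instructions' STOP-BANG correctly, but not for those who skip or mis-score it; the follow-up form could tell every completer the result.

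*Combined protocol and SAP*

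**What the plan says.** All references are to the combined protocol and SAP.

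- **Risk Category** accepts that a subject may have undiagnosed OSA and says that "this risk is lowered by participating in the study and taking a survey to indicate the level of the risk".
- **Obstructive Sleep Apnea (OSA)** says the instructions for use help users judge their own OSA risk and may prompt a home sleep study.
- **Methods and Procedures** places STOP-BANG (Attachment D) in the product instructions and attaches the action to that copy: "If they are determined to be high-risk by the self-administered questionnaire, they will be given the following options". The options are an in-office sleep study, a discounted home sleep study, or returning the device for a refund.
- **Data Collection** puts STOP-BANG in the follow-up form but not the baseline form: "The postquestionnaire will consist of Attachments B, C, and D". The reason given is the study's own use: "also allowing the study to evaluate the response of subjects at high risk of OSA".
- **Study Design** says that at follow-up "users will be asked if they self-identified (on the basis of the product instructions) as being at risk for OSA", and then "If they answer positively, they will be asked about their response".
- **Alternatives to Participation** says that if severe OSA is suspected, "patients are encouraged to go through a sleep study to conclusively diagnose sleep apnea".
- **Costs to the Subject** makes the $90 refund depend on completing the follow-up survey. **Transition from Research Participation** has subjects continue with the device under its instructions and stop when they wish.

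**The concern.** STOP-BANG reaches a subject twice. The first time is in the instructions, where subjects score themselves and high-risk subjects are given options. The second is in the follow-up form, where the study receives the answers and no stated step gives anything back.

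A subject who skipped or mis-scored the first copy can say at follow-up that they did not self-identify as at risk. They can then give STOP-BANG answers that indicate high risk, collect the refund and keep using the device. The study would hold the evidence of risk and the subject might not know it. Purpose and Background raises the worry that an over-the-counter device could keep people from a sleep study, so this group matters to the plan's own argument.

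What is at stake is subject protection and the accuracy of one risk statement. The VAS and Snoring Severity Scale comparisons are not involved. Nor is it a complaint that the self-score goes unchecked: how people respond to the instructions unaided is part of the over-the-counter behavior the trial sets out to observe.

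**Working it through.** This is mainly a question of text, so the check follows two subjects through the stated steps.

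**Subject A completes the instructions copy correctly and is high-risk.**
1. The self-score indicates high risk and the three options apply (Methods and Procedures).
2. If still in the study at follow-up, A reports having self-identified and is asked what they did (Study Design).
3. A has been told. The Risk Category sentence is true for A.

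**Subject B would score high but skips or mis-scores the instructions copy.**
1. No high-risk self-score, so the options are not triggered (Methods and Procedures).
2. At follow-up B answers no to self-identification. The further questions are stated only for those who answer yes (Study Design).
3. B completes STOP-BANG in the follow-up form (Data Collection). Its stated purpose is the study's evaluation.
4. The only stated event after the survey is the refund (Study Design, Methods and Procedures, Costs to the Subject).
5. Identified data stay with the coordinator. The investigator receives a subject's data only for an unexpected serious reaction, so a high score opens no route (Data Storage and Confidentiality).
6. B may continue use (Transition from Research Participation).
7. The sleep-study encouragement in Alternatives to Participation is not tied to the follow-up score.

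No stated step tells B the result.

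**Reach of a notice at follow-up.** Inputs are from Data Analysis and Monitoring: 500 enrolled, 30% dropout, about 350 completers.
- Plan's figure: 350 / (1 − 0.30) = 500. It reproduces.
- Not reached: 500 × 0.30 = 150. The plan's dropout allowance includes subjects in whom moderate to severe OSA is discovered, so some of these would already know.
- Reached: 500 − 150 = 350, and 350 / 500 = 70%.

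**Number affected.** This would be completers × the share who skip or mis-score the instructions copy × the share of those who score high at follow-up × the share of those not alerted by the form itself. The documents give none of the three shares, so no count is calculated.

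**The case against.** A reader might infer that the Risk Category sentence has no support. The documents do not bear that out. The survey it mentions is most naturally the copy in the instructions. The OSA background section says those instructions help users judge their risk, and Methods and Procedures attaches options to a high score. The sentence also credits taking part in the study, not the survey alone. This objection stands, and it limits the point to subjects who skip or mis-score that copy.

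Second, the gap may be smaller than it looks, or absent. Both uses are the same Attachment D, which Methods and Procedures describes as self-administered. If it carries a scoring key, a completer meets it again at follow-up and may see the result then. Attachment D and the instructions are not in the supplied text and the consent pages were removed, so this cannot be ruled out. The follow-up question about self-identification also points the subject back to the instructions. This stands as a limit on confidence.

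Third, a notice that repeated all three options would confuse, because completers are refunded anyway. That is right, and the fix leaves the return option out.

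Fourth, an email route has the coordinator sending results, a task the plan does not assign, and identifiers are to be removed before analysis. The coordinator already holds the identifiers, and an individual reply can go out before they are removed. The plan need only add the task.

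The absence of any stated feedback of the follow-up result survives all four.

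**Conclusion.** The concern holds in a limited form. The Risk Category statement is supported for subjects who complete the instructions copy correctly and unsupported for those who do not. The follow-up form is the one stated point at which the study could give every completer a result, and the supplied text does not use it.

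This is an optional, low-cost improvement. A notice would reach about 350 of 500 subjects if the plan's 30% dropout holds. The number who would otherwise finish uninformed is unknown and may be small.

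A reader might apply the background OSA shares, 10% of male and 22% of female snorers, to 350 completers and infer that 35 to 77 people are left uninformed (350 × 0.10 = 35; 350 × 0.22 = 77). The documents do not support that. Those shares describe OSA among snorers in general, not high STOP-BANG scores among people who skipped or mis-scored a form. The trial also excludes diagnosed sleep apnea and drops those who seek a sleep study or return the device.

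The conclusion assumes that Attachment D, the instructions and the consent form contain no step that already returns the follow-up result.

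**What to change.** 1. After the VAS, Snoring Severity Scale and behavior items are submitted and locked, have the follow-up form display the STOP-BANG risk category, using whatever cut-off the instructions use (the supplied text does not give it). Locking first means the display cannot alter those answers.
2. For high-risk completers, add advice to obtain an in-office or discounted home sleep study and to consider stopping use. Omit the return-for-refund option.
3. Where email forms are used, have the coordinator send the same information as a templated reply, and add this task to Data Storage and Confidentiality.
4. Record that the result was shown or sent. If Attachment D already shows a score, say so in the plan and record that instead.
5. Reword the Risk Category sentence to say that subjects can assess their OSA risk with the survey in the instructions, and that those who complete the follow-up are told their result from it.

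The cost is a small form change, or up to about 350 templated replies, plus the added text. The documents give no cost figure. Alpha, power and sample size do not change. Any later question about seeking care would have to treat the displayed result as a prompt; the plan describes no later survey. The change adds no protection during the ten nights, does not verify the self-score and does not reach the roughly 150 expected dropouts.
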